Post-discharge hospital utilization, i.e., readmissions and ED visits, represent a costly failure of medical care, especially among diabetic patients.[11-13] Patients with diabetes represent about 9% of the US population,[14] but they account for 23% of hospitalizations (over 8 million per year).[15, 16] The number and proportion of hospitalized patients with diabetes has increased steadily over the past two decades,[15, 17, 16] mirroring the increasing incidence and prevalence of diabetes in the general population.[18, 19, 14] While the overall 30d readmission rate is 8.5-13.5%,[20, 21] the 30d readmission rate of diabetic patients is 14.4-21.0%.[22-25] In 2012, costs associated with the hospitalization of diabetic patients in the US were \$124 billion of which an estimated \$25 billion was attributable to 30d readmissions.[26, 27, 15] ED visits of patients with diabetes also impose significant costs to health systems.[28] Reducing 30d readmissions among diabetic patients has the potential to greatly reduce healthcare costs. **A modest 5% reduction in the 30d readmission rate would result in 82,754 fewer admissions per year, translating into an estimated annual cost savings of \$1.2 billion.**[26, 16] Starting October 1, 2012, the Centers for Medicare and Medicaid Services decreased payments to hospitals that have greater-than-expected 30d readmission rates, reflecting an effort to improve care while reducing costs.[29] These data and the widespread interest in healthcare reform have prompted recent calls for more research on how to prevent 30d readmissions in this important group of patients.[30-32]

Identifying and intervening in the highest risk diabetic patients to reduce readmission rates may have a large impact. Such an approach, colloquially known as “**medical hot-spotting,**” has been successfully applied in a socioeconomically disadvantaged population to reduce hospital utilization in

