a) Recruitment Methods

We will recruit study subjects as follows:

1. We will review a daily computer-generated admission log of patients admitted to medical-surgical units at TUH who have been ordered for routine glucose testing. This captures most patients with recognized diabetes.
2. We will review the medical chart of patients on the admission log to determine potential eligibility. We request a waiver of consent and HIPAA to identify candidates. We will access only the minimum data needed to obtain this information.
3. We will request permission to approach the potential subject about the study from a physician on the primary team providing hospital care.
4. Study participants will be provided \$50 after 30 days of follow-up has been completed and outcomes have been assessed. Subjects who also provide an in-depth interview after the follow-up period will be given another \$50.

b) Inclusion and Exclusion Criteria

Screening for eligibility will be performed by chart review and brief history of the potential subject.

Inclusion criteria

1. Diabetes, defined by pre-admission use of a diabetes-specific medication and/or documentation of the diagnosis in the medical record.
2. Age 18 years or older at the time of admission
3. Admission to a non-critical care unit

Exclusion Criteria:

1. Female subjects who are pregnant and/or admitted to an obstetric service

Readmission Pilot Trial

2. Binge drinking (5 or more alcoholic drinks for males or 4 or more alcoholic drinks for females on the same day) or drug abuse within 3 months before admission
3. Receiving palliative care during the hospitalization
4. Participation in another readmission risk reduction program
5. Inpatient death
6. Planned or actual transfer to another hospital or subacute facility
7. Discharge to hospice or a long-term care facility
8. Discharge by signing out against medical advice
9. Discharge expected within 12 hours or admission to a short-stay unit
10. Lack of access to a phone
11. Living more than 30 miles away from TUH
12. Mental condition rendering the subject unable to understand the nature, scope, and possible consequences of the study
13. A1c <5.7%
14. Inability to speak English

c) Local Number of Subjects

Up to 300 subjects will be enrolled locally across the following study groups: 60 subjects in the intervention group, 60 in the high-risk control group, and 180 in the low-risk control group.

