We estimate that 25% of screened patients will not meet eligibility criteria, which means that at least 300 patients will be screened.

d) Study Timelines

Subjects will be enrolled during their hospital stay and will participate in the study for 3 months following hospital discharge. The intervention will be delivered during the 4 weeks following discharge. Final assessment for outcomes will be performed at 3 months after discharge. We anticipate enrollment will occur between July and December of 2019. We estimate that primary analyses will be completed by June of 2020.

e) Study Endpoints

The primary outcome will be the number of initial hospital readmissions within 30 days of discharge. Secondary outcomes will also be assessed at 30 days of discharge unless otherwise specified. Secondary outcomes will include:

1. time to first readmission
2. number of emergency department (ED) visits
3. a composite of 30d readmissions and ED visits

Readmission Pilot Trial

4. number of primary care and specialist provider follow-up visits scheduled and attended
5. incidence of medication review or reconciliation post-discharge
6. cost of post-discharge care as a sum of ED visits, readmission, home health services, and outpatient provider visits
7. cost of the intervention
8. subject experience assessed by a brief questionnaire
9. self-monitored blood glucose levels and frequency of testing
10. change in well-being from baseline to 5 weeks after discharge as measured by the World Health Organization Well-Being Index (WHO-5).[43]
11. change in diabetes-related distress at 5 weeks after discharge as measured by the Problem Areas in Diabetes (PAID) scale.[44]
12. change in perceived social support at 5 weeks after discharge as measured by the Multidimensional Scale of Perceived Social Support (MSPSS).[45]
13. change in perceived stress at 5 weeks after discharge as measured by the perceived stress scale (PSS).[46]
14. change in diabetes knowledge at 5 weeks after discharge as measured by the Diabetes Knowledge Test (DKT2).[47]
15. change in A1c level from baseline to 3 months after the index discharge

f) Procedures Involved in the Human Research

After enrollment, subjects will be sorted into 2 groups based on the predicted risk of readmission by the DERRI: high risk and low risk (Figure 1).

[figure not shown]

Figure 1. Allocation of study participants

Low-risk group:

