4) Post-discharge support: At 24 to 48 hours post-discharge, a nurse Navigator will call the patient to assess the patient’s status, confirm receipt of and compliance with medications, verify the follow-up appointment schedule, assess for barriers to following the discharge plan, determine the need for a community health worker (CHW) referral, and review blood glucose control (patients who are discharged on non-insulin regimens will be expected to test their blood glucoses at least once a day, and patients who are discharged on an insulin regimen will be expected to test their blood glucoses at least twice a day). Similar phone calls will be made weekly for four weeks following discharge by a Navigator. If a patient reports significant high or low blood glucose levels, then the PI or a co-Investigator (Endocrinologists) will call the patient to adjust diabetes therapy (See Tables 1a and 1b for insulin dose adjustment protocols). Eligible patients will receive a referral for a nursing visit from a local home care agency to assess medical needs for support at home and medication reconciliation. Referral to a CHW may be made if subjects are found to have non-medical needs and/or obstacles to maintaining self-care and attending follow-up appointments. Such non-medical support might include transportation to and from medical appointments, food, housing, or legal assistance, relief from utility bills, verification of insurance, support groups and delivery of durable medical equipment.

Table 1a. **Outpatient basal insulin dose adjustment:**

Basal Insulin	
If mean FBG > 180 mg/dL for the last 2 consecutive days and no episodes of hypoglycemia	Increase daily basal dose by 4 IU
If mean FBG > 140 mg/dL for the last 2 consecutive days and no episodes of hypoglycemia	Increase daily basal dose by 2 IU
If mean FBG between 100 to 140 mg/dL for the last 2 consecutive days and no episodes of hypoglycemia	No Change
If any FBG between 70 – 99 mg/dl	Decrease by 4 IU or 10% of total daily basal dose
If any FBG < 70 mg/dl	Decrease by 8 IU or 20% of total daily basal dose
If any FBG < 40 mg/dl	Decrease total daily basal dose by 30%

FBG=Fasting blood glucose; Hypoglycemia=typical symptoms (e.g., sweating, tremor, acute hunger, anxiety) and/or blood glucose <70 mg/dL

Table 1b. **Outpatient prandial/pre-meal insulin dose adjustment based on subsequent mealtime/HS BG values:**

Pre-meal Rapid Insulin		
Pre-meal Dose, U	BG 70 – 100 mg/dl*	BG 141-180 mg/dl**

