All data collected by the research team will be considered part of the participant's confidential record. Data collected on paper from research participants will be placed in a locked file cabinet in the GCRC within 24 hours. The destruction date of paper files will be at least 7 years from the termination of the study and will be authorized by the PI. Access to research and confidential records will be limited to clinical investigators and research coordinators.

h) Data Management

Statistical analysis: Distributions of the data will be assessed by descriptive statistical and graphical methods. To assess the randomization procedure, baseline values of all variables will be compared between the intervention and usual care group. Between-group differences for continuous variables will be compared using the Wilcoxon test. Proportions will be compared between groups using the chi-square test or exact tests when expected cell counts are less than 5. The primary outcome of 30d readmission rate will be compared between intervention and control groups with the chi-square test. Point estimates of 30d readmission rates will be obtained and presented with 95% confidence intervals. Time to readmission will be estimated by Kaplan-Meier curve and compared between groups by log-rank test. The composite of 30d readmission and ED visits will be compared by Cox regression model. Continuous secondary outcomes will be compared using Wilcoxon test. Categorical secondary outcomes will be compared using chi-square test. The primary analyses for all outcomes will be performed in the intention-to-treat (ITT) population. Secondary analyses for all outcomes will be performed in a per-protocol population restricted to subjects who complete at least one follow-up phone call. In addition, outcomes will be assessed for differences by the number of follow-up phone calls

Readmission Pilot Trial

completed (dose-response analysis). Lastly, all outcomes will be assessed in the ITT subgroup of subjects with a baseline A1c >7%. Statistical significance will be claimed at an alpha level of 0.05.

Power analysis: The sample size for Phase 2A was based on an expected drop-out and post-enrollment exclusion rate of 25% as well as the capacity of the research team. Because this is a pilot feasibility trial, the study is not powered to detect a difference in outcomes.

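### The Wilcoxon rule also covers the cost of post-discharge care, where a rank test does not compare mean cost and can point the opposite way

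*Protocol*

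**What the plan says.** Protocol section 8e lists 15 secondary outcomes, assessed at 30 days unless stated otherwise. Item 6 is "cost of post-discharge care as a sum of ED visits, readmission, home health services, and outpatient provider visits". Item 7 is "cost of the intervention".

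Section 8h (Statistical analysis) gives one rule for outcomes of this type: "Continuous secondary outcomes will be compared using Wilcoxon test". It adds that "Statistical significance will be claimed at an alpha level of 0.05". Cost is not excepted. The only confidence intervals named are those for the 30-day readmission rates. The randomised comparison is between the first two groups in section 8c: "60 subjects in the intervention group, 60 in the high-risk control group, and 180 in the low-risk control group".

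The reason for interest in cost is in section 5 (Significance): "A modest 5% reduction in the 30d readmission rate would result in 82,754 fewer admissions per year", which the protocol converts to about $1.2 billion a year.

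Section 8f describes two parts of the intervention that bear on item 6. Under post-discharge support, "Eligible patients will receive a referral for a nursing visit from a local home care agency". Under peri-discharge coordination, a Navigator confirms follow-up appointments and helps with barriers to attending them. Home health services and outpatient visits are both counted in item 6.

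**The concern.** A saving for a health system is the mean cost difference per patient multiplied by the number of patients. A Wilcoxon test instead asks whether a random intervention subject tends to cost more than a random control. It sees that a readmission ranks above an outpatient visit, but not that it costs many times as much.

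Thirty-day cost has a shape for which these two questions can have different answers: small amounts for most subjects and very large amounts for the readmitted minority. If the intervention prevents a few readmissions but adds a visit or a nursing call for many others, the mean can fall while the ranks rise.

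The pilot is meant to inform a definitive trial. A rank p-value pointing towards higher cost, with no mean difference beside it, would be a poor guide to whether post-discharge cost fell.

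**Working it through.** The protocol states no standard deviation, power or expected difference for cost, so there is no figure to reproduce. The check asks whether the reversal can occur and how often.

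**Inputs from the protocol**
- Cost per readmission: $1.2 billion / 82,754 = about $14,501 (section 5).
- Control readmission rate: 14.4% or 21.0%, the range given for patients with diabetes (section 5).
- Relative reduction in readmission: 30% or 50%, within the 30% to 75% cited (section 5).
- 60 per arm (section 8c), or 60 × 0.75 = 45 after the 25% loss in section 8h.
- Alpha 0.05, taken as two-sided because the protocol does not say.

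**Assumed inputs**
- A third control rate of 30%, for a group selected as high risk.
- Outpatient visits at $150, with a mean of 1.0 per control subject.
- Home nursing at $300, in 20% of controls.
- An ED visit at $1,000, in 15% of both arms.
- Readmission cost skewed (gamma, shape 2, mean $14,501).
- Added low-cost care in the intervention arm: none; modest (1.4 visits, 35% nursing); or larger (1.8 visits, 50% nursing).

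**Step 1: a fixed example, 60 per arm.** Control: 13 readmitted, and every subject has $150 of outpatient care. Intervention: 9 readmitted, and every subject has $450.
- Control mean = (13/60) × 14,501 + 150 = $3,292.
- Intervention mean = (9/60) × 14,501 + 450 = $2,625, which is $667 lower.
- Medians are $150 and $450.
- Pairs in which the intervention subject costs more: 9 × 47 + 9 × 13 + 51 × 47 = 423 + 117 + 2,397 = 2,937 of 3,600, or 82%.
- Wilcoxon p = 1.3 × 10⁻¹⁰, towards higher cost with the intervention.

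This example is extreme because outpatient cost does not vary within an arm. It shows that reversal is possible, not that it is likely.

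**Step 2: true saving in the simulation.** Saving = control rate × relative reduction × 14,501 − added care. Added care is 0.8 × 150 + 0.30 × 300 = $210 (larger), 0.4 × 150 + 0.15 × 300 = $105 (modest), or $0. For example, at 21% and 30%: 0.21 × 0.30 × 14,501 = $914, less $210 = $704.

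**Step 3: wrong-way significance.** The table gives the share of 1,500 simulated trials, 60 per arm, in which Wilcoxon was significant for higher cost with the intervention. The true mean saving is in brackets.

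| Control rate, relative reduction | Larger added care | Modest | None |
|---|---|---|---|
| 14.4%, 30% | 57.7% ($416) | 18.4% ($521) | 0.8% ($626) |
| 21%, 30% | 42.8% ($704) | 9.4% ($809) | 0.7% ($914) |
| 21%, 50% | 30.3% ($1,313) | 5.5% ($1,418) | 0.1% ($1,523) |
| 30%, 30% | 18.9% ($1,095) | 3.8% ($1,200) | 0.6% ($1,305) |
| 30%, 50% | 9.4% ($1,965) | 1.1% ($2,070) | 0.1% ($2,175) |

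With larger added care, Wilcoxon was significant in the right direction in at most 0.5% of trials. At 45 per arm the larger-care column becomes 49.5%, 32.5%, 23.0%, 15.2% and 8.3%.

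**Step 4: comparing means instead.** In the same settings Welch's t-test was significant in the wrong direction in at most 0.9% of trials at 60 per arm and 1.3% at 45. Its power to show the saving at 60 per arm was only 6% to 37%.

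**The case against.** The strongest case against is that the size of the effect rests on figures the protocol does not give. It states no unit cost or rate for nursing, outpatient or ED visits. It speaks of one nursing visit for eligible patients, and a referral is not uptake. Aim 1 also targets ED visits, which the simulation holds equal between arms.

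This stands. A second model used 30% v 20% readmission; one to three nursing visits at $400 in 20% v 50%; 1.2 v 1.8 outpatient visits at $150; and 0.2 ED visits per patient at $1,000. It gave 13% wrong-way significance. With ED use cut by a third and a single nursing visit, this fell to 7%. With modest added care (35% nursing, 1.5 visits) and ED use unchanged it was 2.8%, against 2.3% in the right direction. With modest added care and ED use cut by a third it was 1.4% against 4.4%.

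It is also fair that this is one of 15 secondary outcomes in a pilot that disclaims power, and that the national savings figure is background, not a stated estimand. Low power does not justify the rank test, though. It makes an estimate with an interval more useful than a p-value.

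A reader might infer four stronger claims, which the document does not support:
- *The intervention saves money overall.* Item 6 leaves out the intervention's own cost, such as Navigator time and the medication supplied under section 16. The simulated savings concern post-discharge care only.
- *The intervention is designed to raise low-end cost.* The protocol describes referral and help with appointments. How much cost these add is unknown.
- *Item 7 will be put through an empty test against zeros.* This cost arises in one arm only, and Navigator minutes are collected to derive it. Nothing says controls will be scored zero and tested.
- *Net cost will never be produced.* The protocol does not forbid reporting means or combining the two costs, and an unseen analysis plan may do so.

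**Conclusion.** The point holds for outcome 6. The protocol fixes a test for it that does not compare mean cost, and that test can point the opposite way to the difference in mean post-discharge cost. The direction error depends on how much low-cost care the intervention adds and shrinks as the effect on readmission grows. Only the readmission cost, two of the three control rates, the range of relative reductions and the sample size come from the protocol. The remaining inputs are assumptions, so the percentages show a range and do not forecast this trial. That the test has the wrong target does not depend on them. Severity is minor to moderate.

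**What to change.** In section 8h, except outcome 6 from the Wilcoxon rule. Report the difference in arithmetic mean 30-day cost per randomised subject, intervention minus usual care, with a bootstrap 95% confidence interval. Show it twice: for post-discharge care alone, and with the intervention's own cost (outcome 7) added in the intervention arm. Report outcome 7 by itself descriptively. A Wilcoxon result for outcome 6 may stay as supportive at most, and the rule can stand for the non-cost outcomes.

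The cost is a sentence or two in section 8h and a few lines of code. Section 8f already lists post-discharge cost and Navigator time among the data collected. The downside is that the interval will be wide at 60 per arm and wider at 45: the change corrects the target and largely removes the direction error, but adds no power.

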≤ 10 U	Decrease by 1 U	Increase by 1 U
>11- 19 U	Decrease by 2 U	Increase by 2 U
≥ 20 U	Decrease by 3 U	Increase by 3 U
Pre-meal Dose, U	BG 40-70 mg/dl x 1	BG 180-240 mg/dl x 1

Readmission Pilot Trial

≤ 10 U	Decrease by 2 U	Increase by 2 U
>11- 19 U	Decrease by 3 U	Increase by 3 U
≥ 20 U	Decrease by 4 U	Increase by 4 U
Pre-meal Dose, U	BG < 40 mg/dl x 1***	BG > 240 mg/dl x 1
≤ 10 U	Decrease by 4 U	Increase by 3 U
>11- 19 U	Decrease by 6 U	Increase by 4 U
≥ 20 U	Decrease by 8 U	Increase by 5 U

Pre-meal insulin dose adjustment is based on the subsequent BG value, e.g., pre-breakfast insulin dose is based on the pre-lunch BG.

* If > ½ of the mealtime/HS BG values for the week were below target.

**If > ½ of the mealtime/HS BG values for the week were above target.

*** Decrease by 30-40% in the event of severe hypoglycemia (mealtime/HS BG < 40 mg/dl).

BG=blood glucose; Mealtime/HS=pre-lunch, pre-dinner, or bedtime

The above algorithm provides recommended insulin doses and may be modified based on clinical judgment of the investigator or co-investigator.

Usual care: Most aspects of the intervention go above-and-beyond usual care. Patients in the usual care group will receive the standard discharge instructions and medication reconciliation process. Those who are new to diabetes receive training by a floor nurse on using a glucometer as well as a stock set of printed educational materials. The floor nurses also train patients who are new to insulin injections as needed. Patients with diabetes are referred to outpatient diabetes education at Temple on a case-by-case basis as determined by the primary hospital provider team. Diabetes therapy upon discharge is decided on a case-by-case basis by the primary team. Discharge instructions are routinely sent to the primary care physician either by fax or EPIC. Most TUH patients receive a phone call 2 to 4 days after discharge from a CHW that includes checking on the status

Table 2. Timeline for assessments of subjects

Visit #	1	2	3	4	5	6	7	8
Time (weeks)	0	2 days	1	2	3	4	5	13
Intervention group								
Phone call/clinic visit								X
Psychometric assessments	X							X
Diabetes knowledge	X							X
30d endpoints								X
Interview							X	
A1C	X							X
Navigator call		X	X	X	X	X		
Blood glucose		X	X	X	X	X	X	
Adverse events		X	X	X	X	X	X	
Usual care group								
Phone call								X
Psychometric assessments	X							X
Diabetes knowledge	X							X
30d endpoints								X
A1C	X							X
Blood glucose								X

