Adverse events								X
Low-risk group								
Chart review/phone call								X
Psychometric assessments	X							X
Diabetes knowledge	X							X
A1C	X							X
30d endpoints								X

Readmission Pilot Trial

of follow-up appointments, confirming access to medications, and answering questions.

Data collection: The following data will be collected at baseline: A1c, sociodemographics, medical history, including HIV, substance abuse, and mental health status, which are likely risk factors for admission, relevant laboratory results, admission diagnoses, self-reported goals for health and diabetes, well-being (WHO-5), diabetes-related distress (PAID scale), perceived social support (MSPSS), perceived stress (PSS), diabetes knowledge (DKT2), depression screening by the PHQ-2/9, and health literacy by the BHLS (Table 2).

The following data will be collected during follow-up: A1c, discharge diagnoses, hospital readmission (date, primary diagnosis), ED visits (date, primary diagnosis), physician follow-up appointments scheduled and/or attended, post-discharge medication reconciliation (yes/no), cost of post-discharge care, self-monitored blood glucose levels, Nurse Navigator time to deliver the intervention (minutes), well-being (WHO-5), diabetes-related distress (PAID scale), perceived social support (MSPSS), perceived stress (PSS), diabetes knowledge (DKT2), depression (PHQ), and patient experience according to a brief questionnaire (**Appendix Item 3a [usual care] or 3b [intervention]**). These follow-up data will be collected during a phone call about 5 weeks after the index discharge. Baseline and 3-month post-discharge A1c levels will be obtained as part of standard-of-care. A letter reminding patients to do the 3-month blood draw for the A1c test will be sent by mail.

Data will be collected by phone interviews with subjects and review of the electronic medical record (EMR). The Research Specialist will be primarily responsible for screening and recruiting subjects, data collection and data entry.

Phase B: Qualitative evaluation of intervention

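### The call-based per-protocol set filters the two randomised arms differently, so its between-arm comparison can be biased in either direction

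*Protocol*

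**What the plan says.** The Protocol's section 8 h) (Data Management, Statistical analysis) puts ITT first: "The primary analyses for all outcomes will be performed in the intention-to-treat (ITT) population". It then adds: "Secondary analyses for all outcomes will be performed in a per-protocol population restricted to subjects who complete at least one follow-up phone call". That covers the readmission comparison ("The primary outcome of 30d readmission rate will be compared between intervention and control groups with the chi-square test") and also the log-rank, Cox and Wilcoxon comparisons. The 0.05 significance level is stated without exempting this set. The next sentence says that "outcomes will be assessed for differences by the number of follow-up phone calls" completed, and calls this a dose-response analysis. The qualifying call is not defined.

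The calls themselves are in section 8 f):

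- **Intervention arm** (component 4, Post-discharge support): "At 24 to 48 hours post-discharge, a nurse Navigator will call the patient", and afterwards "Similar phone calls will be made weekly for four weeks following discharge by a Navigator". That makes 1 + 4 = 5 calls. Table 2 lists Navigator calls under the intervention group only.
- **Usual care**: "Most TUH patients receive a phone call 2 to 4 days after discharge from a CHW". This is routine hospital practice and is not among the study data listed under Data collection.
- **Both randomised arms** (Data collection): "These follow-up data will be collected during a phone call about 5 weeks after the index discharge".

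**The concern.** A per-protocol comparison is interpretable only if the rule for staying in the set works alike in both arms, or if the difference is handled in the analysis. Here the qualifying event seems to exist in one arm only. Subjects who never answer a call may be sicker or less well supported than those who do, and a subject back in hospital soon after discharge may be unable to take the first call. Removing such subjects from one arm while their counterparts stay in the other loses the protection of randomisation.

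At stake is a secondary estimate for every outcome, including 30-day readmission, in a pilot whose Aim 1 includes exploring efficacy. A difference produced by selection could be read as an effect among those who actually took part.

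**Working it through.** **Step 1. Which call?** The plan gives no figure for the size or results of this set, so there is nothing to reproduce. The possible readings are:

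| Qualifying call | Effect on the two arms |
|---|---|
| Navigator call, applied literally to both | Usual-care set is empty |
| Navigator call, applied to the intervention arm only | Unreached subjects leave one arm only |
| Any study call | Intervention has about six chances (5 + 1), usual care one, after the 30-day window |
| 5-week call only | Same criterion in both arms, but it measures reachability after the outcome window, not receipt of the intervention |

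The wording requires one call or more, and the next sentence counts calls as a dose. Both fit a series of calls, so the Navigator reading is the most natural.

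**Step 2. Inputs for an illustration with no true effect.**

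- Readmission risk *p* = 21%, the upper end of the 14.4–21.0% that section 5 gives for patients with diabetes. No rate is given for the high-risk group.
- 60 subjects per arm (section 8 c).
- Share reached *q* = 0.90 or 0.75, and risk in unreached relative to reached subjects *k* = 1, 2 or 3. Both are assumptions.

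**Step 3. Only the intervention arm is filtered.** The risk among reached subjects is *p* / (*q* + *k*(1 − *q*)). All controls stay, at 21%. The spurious relative risk is 1 / (*q* + *k*(1 − *q*)). The last column is the share of 200,000 simulated trials in which a chi-square test (0.05, two-sided assumed) falsely favours the intervention; the nominal value is 2.5%.

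| *q* | *k* | Intervention risk | Relative risk | False benefit |
|---|---|---|---|---|
| 0.90 | 2 | 21/1.10 = 19.1% | 0.91 | 4.4% |
| 0.90 | 3 | 21/1.20 = 17.5% | 0.83 | 6.8% |
| 0.75 | 2 | 21/1.25 = 16.8% | 0.80 | 7.4% |
| 0.75 | 3 | 21/1.50 = 14.0% | 0.67 | 14.5% |

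With *k* = 1 the relative risk is 1.00 and false benefit is 2.4–2.5%. Over the same *q* and *k* values, false benefit is 3.9–10.3% at *p* = 14.4% and 5.1–20.7% at an assumed *p* = 30%. Applying one rule with equal reach to both arms brings it back to 2.5–2.6%. ITT gives 2.3–2.7%.

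**Step 4. Controls must complete the 5-week call.** Assume 95% of the intervention arm qualifies through any call and 75% of controls through the one call. At *k* = 2, the intervention risk is 21/1.05 = 20.0% and the control risk 21/1.25 = 16.8%. At *k* = 3, they are 21/1.10 = 19.1% and 21/1.50 = 14.0%. The bias now goes against the intervention.

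**Step 5. Early readmission alone.** Suppose, as an extreme, that everyone readmitted in days 0–2 completes no later call either. With a constant hazard, the share readmitted by day 2 is 1 − 0.79^(2/30) = 1.56%. The remaining risk is (21.0 − 1.56)/(100 − 1.56) = 19.7%, against 21.0%. This source is small.

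**The case against.** The strongest reply is that the call is undefined and could be the 5-week data call. Table 2 lists a phone call separately from the Navigator calls, and both randomised arms have one. The criterion would then be formally the same in each arm, and an SAP could settle it. This stands in part: the Navigator reading is the more natural, but it is not certain. On the 5-week reading, however, the set no longer measures whether the intervention was received, which is what a per-protocol set is for.

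Second, the magnitudes are assumed. This stands. The Protocol gives neither the share reached nor their relative risk. Its 25% in the power paragraph is drop-out plus post-enrolment exclusion, not failure to reach by phone, and lack of phone access is an exclusion criterion. Any one of five calls qualifies, so few subjects may miss them all. The largest shift in Step 3 is 21.0 − 14.0 = 7.0 points, and the standard error of a two-arm difference at 60 per arm is √(2 × 0.21 × 0.79/60) = 7.4 points.

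Third, the analysis is secondary in a pilot declared not powered for outcomes. This also stands, and it limits the weight of the point.

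A reader might infer that the rule manufactures a benefit, or that the trial's main result is compromised. The documents support neither: the direction depends on the reading, there is no bias if reach is unrelated to risk, and ITT is primary for every outcome.

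**Conclusion.** The point holds as a defect in a secondary analysis. On its most natural reading, the rule conditions on an event that only one arm can experience, so the between-arm per-protocol contrast is not protected by randomisation. The bias may run towards the intervention (only that arm filtered) or against it (controls held to the 5-week call). Its size is unknown. The relative risks of 0.67–0.91 rest on assumed reach and assumed excess risk among unreached subjects; they show what is possible and do not forecast this trial. The Protocol also does not say that the per-protocol estimate will set the assumptions of the later definitive trial. It assigns the guiding role to the Phase B interviews, so a claim that a distorted effect will be carried forward goes beyond the text.

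**What to change.** In section 8 h), replace the per-protocol sentence with one stating that results by completion of at least one Navigator call will be described within the intervention arm only, that this set will not be tested against usual care, and that all between-arm conclusions rest on ITT. The cost is one sentence and the loss of one secondary comparison; no new data are needed.

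A complier-average estimate (the ITT risk difference divided by the share completing a call) should not be the main replacement. It assumes that assignment has no effect on subjects who complete no call. Section 8 f) contradicts this: discharge education can take place in hospital, and diabetes therapy is adjusted at discharge, so both can reach such subjects. At 75% completion the estimate would multiply the whole ITT difference by 1/0.75 = 1.33 and credit it to those who completed a call. Nor would it cover the time-to-event and rank-based outcomes to which the per-protocol rule also applies.
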